### Abstract

The long head of the biceps can be a source of anterior shoulder pain that is primarily due to inflammation or instability of the long head of the biceps (LHB) tendon.

Patients that fail non-operative management become candidates for biceps tenotomy and tenodesis. Currently, there is no universal protocol or gold standard for how the LHB tendon is tensioned. At our institution, the LHB is tensioned based on individual surgeon feel for the correct tensioning. The purpose of this study is to conduct a randomized, single-blinded prospective study comparing patients of the current regimen of bicep tensioning vs. utilizing a standardized method of anatomically tensioning the LHB tendon. The primary aim of assessing change in the American Shoulder and Elbow Surgeon (ASES) scores from baseline to post-surgery between the control and intervention groups will be assessed using a student's t-test. In addition, longitudinal mixed effects models will be used to estimate changes in ASES scores, over all time-points using a random effect for surgeon. Other relevant patient characteristics such as age, sex, and Charlson score will be included to explore the adjusted relationship of the intervention and outcomes over time. A secondary aim of this study is to collect specific measurements of the myotendinous junction of the LHB tendon to potentially establish if any characteristics predispose patients to developing pathology of the LHB tendon.

### I. Background and Significance/Preliminary Studies

Pathology involving the long head of the biceps (LHB) tendon is an established source of upper extremity pain. Biceps tendon pathology is often associated with other primary shoulder pathologies including subacromial impingement, rotator cuff tears, or stenosis of the bicipital groove. The histological findings of the extra-articular portion of the LHB tendon indicate that it undergoes a chronic, degenerative process much like other tendinopathies of the body, such as de Quervain's tenosynovitis of the wrist.

Management of bicipital tendinopathy, such as tendonitis, is generally treated with conservative measures first, which consists of activity modification, non-steroidal anti-inflammatory drugs, and corticosteroid injections. If the patient fails these modalities of treatment, then surgical intervention is considered [7]. There are

multiple ways to perform the procedure and different techniques to perform the tenodesis. The procedure involves performing a tenotomy (cutting) the LHB at the junction between the tendon and the supraglenoid tubercle (origin of the biceps tendon). Tenodesis (or re-attachment of the tendon at a different site) is performed at some location within the intertubercular groove, but outside of the shoulder joint, using one of many forms of fixation either with an open or an arthroscopic approach. Post-operatively, some patients report persistent shoulder pain, biceps muscle fatigue, and bicipital groove tenderness. Scores on the American Shoulder & Elbow Surgeons (ASES), a functional validated scale, are often used to measure these outcomes.

Clinically, it may be important to consider the site of tenodesis in order to restore tension similar to that of normal physiological function. To date, there is no gold standard for the site and level of tenodesis [1, 3, 4, 6]. The current method for fixation (tenodesis) of the LHB tendon after tenotomy is based on surgeon feel for appropriate tensioning within the bicipital groove. We hypothesize that anatomic tensioning of the LHB during tenodesis will provide improved patient outcomes in the form of reducing anterior shoulder pain, bicipital fatigue, bicipital groove tenderness, and ASES scores.

Additionally, there are no current population studies on the anatomy of the LHB tendon and myotendinous junction. Specifically, detail regarding the myotendinous junction transitional zone has not been described [2, 4, 5], nor whether certain anatomical aspects of LHB tendon and myotendinous junction affect the rate of pathology of the LHB. This research project serves as a means to discover if these anatomical differences have clinical significance by obtaining measurements at the myotendinous junction of the LHB.

## **II. Study Aims**

The main purpose of this study is to determine the clinical impact of restoring the anatomic-tension relationship of the long head of the biceps (LHB) when performing a biceps tenotomy and tenodesis. Specifically, we will investigate whether anatomic tensioning will improve functional outcome scores and decrease postoperative complications. We hypothesize that through a standardized method of anatomically tensioning the LHB tendon during tenodesis, patient outcomes will improve.

Another purpose of this study is to provide further information referencing the longitudinal anatomy of the LHB, specifically at the myotendinous junction transition zone. There are multiple measurements that are unique to each individual. The measurements that we will analyze are the length from the supraglenoid tubercle to both the proximal and distal extents of the myotendinous junction. From these two measurements, we can calculate the total length of the myotendinous junction from beginning of muscle fibers to the end of tendinous fibers. We will also measure the width and circumference of the myotendinous junction.

To date, these particular measurements have never been done before in an *in vivo* fashion. Our hope is that this analysis of the LHB myotendinous junction will identify any relationships with pathology at the LHB tendon.

### **IV. Study Design**

- a. Experimental Design: Patients that meet the inclusion/exclusion criteria will be eligible for participation in the study. The design will be a single blinded format where the surgeon will be aware of what treatment the patient will receive (Control vs. Intervention). The patient will not be informed of what arm of treatment they were selected for. Block randomization will be utilized to place an equal number of patients into both groups.
- b. Study Population: Patients undergoing arthroscopic shoulder surgery with long head of the biceps tendon pathology.
- c. Sample size determination and power analyses:  
Based on previous studies, it is assumed that the pre-ASES score for all patients undergoing biceps tenodesis is approximately 45. At 1 year post surgery, the standard of care group will increase to 85 (Mean difference = 40, STD=18). It is hypothesized that the treatment group with anatomical fixation will increase to approximately 93 (Mean difference = 48, STD=18).

The necessary sample size was calculated using 80% power of rejecting the null hypothesis (that there is no difference in change in ASES scores between the two groups of interest), when the population mean difference in ASES is  $\Delta 1 - \Delta 2 = 48 - 40 = 8$ , with a standard deviation of 18, and with a significance level (alpha) of 0.05. This power and sample size calculation was computed using a two-sided two-sample equal-variance t-test.

To achieve this power, at least 81 patients will need to be enrolled in each group. Patients will only be randomized once to this study. If a patient has a repeat surgery, that case will not be eligible for randomization.

- d. Study outcomes/endpoints
  - i. Study endpoint will be decided based on the power analysis that was calculated by the research team biostatistician.
  - ii. Data collected:
    1. Demographics: Name, MRN, age, sex, hand dominance, ethnicity, profession, BMI

2. Clinical Factors: Indication for surgery, procedures performed, past medical history of upper extremity pathology
3. Medical History: Myocardial infarction, congestive heart failure, peripheral vascular disease, transient ischemic attack or cerebrovascular accident, dementia, chronic obstructive pulmonary disease, connective tissue disease, peptic ulcer disease, liver disease, diabetes, hemiplegia, chronic kidney disease, solid tumor, leukemia, lymphoma
4. Measurements: (in mm)
  - a. Supraglenoid tubercle to end of myotendinous junction (most distal tendinous fibers)
  - b. Supraglenoid tubercle to start of myotendinous junction (most proximal muscle fiber)
  - c. The width of the long head of the biceps tendon at the mid portion of the myotendinous junction

## V. Study Procedures

- a. Subject selection procedures
  - i. Sampling plan
    1. Inclusion criteria:
      - a. Patients at least 18 years of age undergoing arthroscopic shoulder surgery
      - b. Operations that occur at Loyola University Medical Center (Maywood, IL), Loyola Ambulatory Surgery Center (Maywood, IL), or Gottlieb Memorial Hospital
    2. Exclusion criteria:
      - a. Previous shoulder surgery involving the long head of the biceps tendon
      - b. Younger than 18 years old
      - c. Current pregnancy
        - i. As per standard protocol with all surgeries, a urine pregnancy test is performed prior to surgery. If positive, the surgery will be cancelled and the patient will be excluded from the research study.
  - ii. Recruitment procedures
    1. Where will recruitment occur?
      - a. During the patient's initial clinical visit, qualifying patients will be identified by [name] or [name] and will be approached for voluntary study participation. At that time, they will be given a written document for informed consent. The clinician will go over the consent and the patient will have the opportunity to ask any questions. If they agree to be in the study, then informed consent will be

obtained then. If they wish to read over the consent further and make a decision later, then they will be approached on the day of surgery by a member of the research team. If they decide against the research study, then they will continue to receive the standard of care as per usual.

- b. If the patient wished to read the informed consent further at the clinical visit prior to making a decision, then they will be approached on the day of surgery by a member of the research. Once again, the entirety of the research project will be explained to the patient. If they wish to proceed, then written consent will be obtained. If they decide NOT to participate in the study, then they will continue on to surgery and receive the standard of care.

2. Who will obtain consent?

- a. If obtained at the initial clinical visit, then it will be obtained by [name] or [name].
- b. If obtained on day of surgery, then a member of the research team will obtain the written consent.

3. What recruitment materials will be provided to the potential participant (brochures/information sheets/video presentation)?

- a. At the patient's initial clinical visit, they will be given a copy of the informed consent that details specifics of the research study that we are conducting. It will be translated into a health comprehension level deemed appropriate by the IRB committee (7th grade).

- iii. Screening procedures

1. What procedures are required for screening?

- a. At the initial outpatient office visit, qualifying patients will be further screened using the aforementioned inclusion/exclusion criteria. At that time, [name] or [name] will speak with the patient about the research study to its entirety, which will include the potential benefits, risks and alternatives.

2. What is the screening schedule (number of visits, length of visits)?

- a. Patient will be screened during their initial outpatient office visit.
- b. Those patients that express interest will again be approached on the day of surgery. On this day, a member of the research team will explain to the patient, for the second time, the research project.

3. Which screening tests/procedures are part of standard care and which are for research purposes only?

- a. A member of the research team will be at the office visit to obtain an ASES score prior to surgery and will contact patients via phone at 2 weeks, 6 weeks, 3 months, and 6 months and one year after surgery.
  - b. Standard of Care: Aspects of the physical examination including range of motion, strength, neurovascular status, and shoulder/elbow specific testing will be recorded by the surgeon in the chart per standard history and physical documentation.
    - i. A member of the research team will gather this information via chart review.
  - c. Research Specific: On the day of surgery, a member of the research team will ask the patient a short series of questions in order to calculate an American Shoulder & Elbow Surgeon (ASES) score as their preoperative score. The member of the research team administering the questionnaire will not be blinded. A specific description of the ASES questionnaire is detailed later in the protocol. This questionnaire will again be tested at the patient's 6 month follow up.
4. What happens with screen failures (including any data gathered during screening)?
  - a. Those patients that are not eligible based on the inclusion/exclusion criteria, will not be included in the study.
  - b. The risk of patients incorrectly being included in the study despite screening the inclusion/exclusion criteria is essentially zero.
    - i. All female patients are screened day of surgery with a pregnancy test.
    - ii. Age of patient is obtained & confirmed at all clinical encounters.
    - iii. History of prior surgery is obtained and verified at initial clinical visit.
- b. Randomization procedures
  - i. Surgeon block randomization scheme will be used. This will be 1-1 stratified for [name] and [name].
  - ii. Each surgeon will receive a stratified block randomization list provided by the department of Biostatistics and will be used for patients in chronological order for the surgical start time. Both surgeon schedules are accommodating of this because they are in the operating room on different days of the week.
  - iii. Prior to the start of the surgery, the surgeon will be notified by a member of the research team if the patient will be part of the control group or the anatomic fixation group.

- c. Study Intervention
  - i. Control Group: The control group patient will undergo biceps tenotomy and tenodesis based on surgeon feel on appropriate tensioning of the tendon (Current practice).
    - 1. Of note, there is no universal method or gold standard on how the long head of the biceps should be tensioned during bicep tenodesis.
  - ii. Intervention Group: Patients that are randomized to the intervention group will undergo biceps tenodesis in a standardized, step-by-step protocol as outlined below
- d. Surgical Procedure Overview
  - i. The initial indication for tenodesis is at the surgeon's discretion, but after that decision is made, then the Control vs. intervention is determined based on our randomization scheme.
  - ii. Per current surgeon protocol, all patients will receive a single injected pre-operative nerve block and standard post-operative pain regimen.
  - iii. As with every shoulder arthroscopy, a diagnostic scope of the shoulder will be performed, which will include evaluation of the intra-articular portion of the long head of the biceps tendon. If there is any instability or tendinopathy, then the surgeon will decide if biceps tenotomy and tenodesis is indicated.
  - iv. Surgical Steps: Biceps Tenotomy & Tenodesis

\*Bolded steps are deviation from current, standard surgeon protocol

1. Positioning of the patient will be in the standard beach chair position
2. During the diagnostic arthroscopic shoulder scope, the long head of the biceps is inspected for any instability or tendinopathy, which would be an indication to perform tenotomy at the junction of the supraglenoid tubercle with arthroscopic scissors
  - a. If Control group: Bicep tenotomy will occur now
3. The patient will undergo all other indicated arthroscopic portions of the case (i.e. rotator cuff repair, subacromial decompression, rotator interval release, etc.)
4. At the conclusion of the arthroscopic portion of the case, the patient's arm will be placed with the elbow at 90 degrees of flexion and neutral forearm rotation. ***The trochar in the anterior shoulder portal and the arthroscope in the posterior shoulder portal will be left in the glenohumeral joint momentarily. The arthroscopic light will be shut off temporarily. Both will be secured to the shoulder using sterile ioban to maintain a good water seal & ensure that both are kept in the correct position for tenotomy later***
5. The standard mini-open subpectoral approach will be made along the anterior axillary fold
6. Full thickness skin flaps are developed down to muscular fascia

7. The biceps fascia is opened and the pectoralis major tendon is retracted superiorly
8. *The myotendinous junction of the long head of the biceps tendon and its location within the intertubercular groove will be marked using electrocautery*
9. *The surgeon will then turn back to the glenohumeral joint, remove the ioban, turn the arthroscope back on, then perform the biceps tenotomy. All instrumentation will be removed from the glenohumeral joint at this time*
10. *The surgeon will then turn to the mini-open subpectoral incision that was previously made and the long head of the biceps tendon will be retrieved*
11. **A ruler will be used to measure the entire length of the long head of biceps tendon from origin to end of tendon fibers, origin to beginning of tendon fibers, and width of the tendon**
12. **The arthroscopy camera will be used to take pictures of the biceps tendon at the myotendinous junction next to a ruler for scale**
  - a. Per standard protocol, these arthroscopic pictures will be inserted into the electronic medical record. This data will be retrospectively collected by a member of the research team.
13. The tendon is tagged with a running, locking number 2 fiberwire suture at the mid substance of the myotendinous junction *using the previously made electrocautery marks to set the tension*
14. The tendon is shortened
15. The sutures from the biceps are passed through the Arthrex cortical button
16. The pectoralis major tendon is retracted and 2 centimeters proximal to the distal insertion a unicortical bone tunnel is drilled in the bicipital groove with a 3.2 millimeter drill
17. The wound is irrigated and the biceps button is threaded into this tunnel and then flipped. The suture is tensioned, securing the biceps against the groove
18. The skin is closed in the usual fashion

e. Study Assessments and Activities

- i. If indicated, patients will undergo biceps tenodesis, as described above
  1. Standard protocol for [name] and [name] is for patients to follow up at 2 weeks, 6 weeks, 3 months, and 6 months after surgery.
    - a. A member of the research team will be at the office visit to obtain an ASES score prior to surgery and will contact patients via phone at 2 weeks, 6 weeks, 3 months, and 6 months and one year after surgery.

- b. A member of the research team will retrospectively collect history and physical examination data using [name] or [name] notes (Complications, Range of motion, strength, special shoulder or elbow physical exam tests).
2. Once the patient has completed their 6 month follow up appointment, all identifiable data from that patient will be deleted from all research records.

[figure not shown]

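### The ASES interviewer is declared unblinded at baseline, and nothing keeps the allocation from those who collect the post-operative ASES; both can be tightened at little cost

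*Combined protocol and SAP*

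**What the plan says.** Section IV.a describes a single-blind trial: the surgeon knows the arm and the patient is not told. Section VIII makes the primary analysis a t-test on change in ASES from baseline.

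On who collects the ASES, and what that person may know:

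- **Baseline.** Section V.a.iii.3.c has a team member question the patient on the day of surgery to obtain the "American Shoulder & Elbow Surgeon (ASES) score as their preoperative score". It then states: "The member of the research team administering the questionnaire will not be blinded". Section V.a.iii.3.a also has an office-visit score: "A member of the research team will be at the office visit to obtain an ASES score prior to surgery".
- **Follow-up.** The same paragraph of V.a.iii.3.c continues: "This questionnaire will again be tested at the patient's 6 month follow up". Sections V.a.iii.3.a and V.e.i.1.a have an unspecified team member telephone patients at 2 weeks, 6 weeks, 3 months, 6 months and one year. Neither says whether the caller is blinded.
- **Allocation.** Section V.b.iii: "Prior to the start of the surgery, the surgeon will be notified by a member of the research team". That person is not specified either.
- **Operative record.** In V.d.iv, step 2a reads "If Control group: Bicep tenotomy will occur now". In the intervention arm, step 8 comes before the tenotomy: "The myotendinous junction of the long head of the biceps tendon and its location within the intertubercular groove will be marked using electrocautery". At step 12, "The arthroscopy camera will be used to take pictures of the biceps tendon at the myotendinous junction next to a ruler for scale", and a team member later retrieves these pictures. Section V.e.i.1.b has a team member review the surgeons' notes.

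**The concern.** Both ends of the primary change score are obtained by a person questioning the patient. If that person knows the arm and this affects how questions are put, how answers are recorded, or what the patient learns about the allocation, the effect becomes part of the between-arm difference. Neither the t-test nor the mixed model can then tell it apart from a treatment effect.

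The plan states that the baseline interviewer is unblinded and is silent on the follow-up callers. It allows one person to relay the allocation, take the baseline score, retrieve the pictures, review the chart and make the calls. It labels the day-of-surgery score as preoperative but does not require it to be taken before the collector learns the arm, although the allocation is relayed that same day.

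**Working it through.** **Reproducing the plan's figure.** Inputs from section IV.c: difference 48 − 40 = 8, SD 18, two-sided alpha 0.05, power 80%, equal-variance t-test.

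- Normal approximation: n = 2 × (1.960 + 0.842)² × 18² / 8² = 79.5, rounded up to 80 per group.
- Exact noncentral t: n = 80.44, rounded up to 81 per group, as stated. Power at 81 is 80.3%.

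The sample size is correct and does not depend on this point.

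**Who may know the arm at each contact.**

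| Contact | Collector | Blinding stated | Kept apart from relaying the allocation |
|---|---|---|---|
| Day-of-surgery ASES (V.a.iii.3.c) | a team member | not blinded | no |
| 6-month repeat (V.a.iii.3.c) | not stated | none; the sentence on being unblinded may extend to it | no |
| Calls from 2 weeks to one year (V.e.i.1.a) | a team member | none | no |

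The pictures and the chart are weaker routes. Only the intervention arm has the cautery mark before tenotomy, but that the mark shows in the step 12 picture is an inference. The documents do not say that the clinic notes record the arm.

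**What a differential interviewer effect would do.** The shifts below are assumed; the documents supply none. Let b be the shift, in ASES points, in the between-arm difference in change, with no true treatment effect and the SD held at 18.

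- SE = 18 × √(2/81) = 2.828; df = 160; critical t = 1.975.
- False-positive rate = P(|T| > 1.975), where T is noncentral t with 160 df and noncentrality b/SE.

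| b (points) | b/SE | b as share of 8 | False-positive rate |
|---|---|---|---|
| 0 | 0 | 0% | 5.0% |
| 0.5 | 0.177 | 6.25% | 5.4% |
| 1 | 0.354 | 12.5% | 6.4% |
| 1.25 | 0.442 | 15.6% | 7.2% |
| 1.86 | 0.658 | 23% | 10% |
| 2.5 | 0.884 | 31% | 14.2% |

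**In units of the scale.** Section V.e.ii gives 5 ASES points per pain point and 5/3 per function-item step. A shift of 2.5 is therefore half a pain point (2.5/5) or 1.5 function steps (2.5 ÷ 5/3), averaged over one arm relative to the other. A shift of 1.86 is 0.37 of a pain point.

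**What partial shielding would do.** If a 2.5-point shift arose only in the half of patients interviewed by someone who knew the arm, the average shift would be 0.5 × 2.5 = 1.25 points and the rate 7.2% instead of 14.2%. The one-half is also an assumption.

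**The case against.** The strongest reply is that this is a declared choice in which the real scorer is already blinded. The design is openly single-blind, the patient is not told the arm, and section V.e.ii fixes the questions and response options. Bias could come only from prompting, mis-recording or disclosure. The documents do not show that any of these would be large, and a 2.5-point average shift would need half a pain point across an arm. All of this stands. It makes the point an improvement and not a contradiction, and leaves the figures as illustration.

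Other objections stand in part:

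- **Baseline timing.** Sections V.d.i and V.d.iii place the allocation after the decision to perform tenodesis, which is made at the diagnostic scope. That makes an informed baseline interview less likely. Section V.b.iii, however, has the allocation relayed before surgery starts, so the route stays open.
- **The one-year call.** The sizing in section IV.c rests on the one-year score. The explicit statement concerns the day-of-surgery interview and is followed only by a 6-month repeat. For one year the concern rests on silence.
- **Missing material.** Some pages were removed from the copy reviewed and the schedule figure in V.e is not shown, so roles or timing may be set there.
- **Pictures and chart.** Both are collected retrospectively, so they need not be seen before a call.
- **Practicality.** A small team may be unable to separate the tasks, and logging adds a field to 5 × 162 = 810 planned post-operative contacts.

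None of this is a reason to leave the callers unshielded. Keeping the arm from them is compatible with the declared design, and it also protects the patient's own blinding.

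**Conclusion.** The concern holds as a design improvement that should be made. The plan states that the baseline interviewer is unblinded. The supplied text neither blinds the post-operative collectors nor separates them from the person who relays the allocation. Both ends of the primary change score are therefore exposed to an effect that analysis could not remove.

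The likelihood and size of such an effect cannot be known from the documents. Under the assumed shifts, half a point to one point does little (5.4% to 6.4%), about 1.9 points doubles the false-positive rate, and 2.5 points brings it to 14.2%. These figures assume no true effect, 81 analysed per arm, and an SD of 18. The stated sample size and power are unaffected.

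**What to change.** 1. **Section V.a.iii.3.c.** Keep the day-of-surgery score as the baseline for the change score and reconcile the office-visit wording in V.a.iii.3.a and V.e.i.1.a with it. Add: *The preoperative ASES is completed before the allocation for that patient is revealed to the person collecting it.* Revise the sentence on blinding to agree.
2. **Sections V.a.iii.3 and V.e.i.1.a.** Add: *Every post-operative ASES, by phone or in person, follows a fixed script, and the arm is not discussed. It is collected by an existing research team member who did not relay that patient's allocation, was not in the operating room, and has not reviewed that patient's operative record or pictures. If this is not possible for a contact, the scripted interview still goes ahead. For each score, record who collected it and whether that person knew the arm.*

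Adverse events heard at a contact are still reported as in section VI. The log also makes possible a sensitivity analysis by whether the collector knew the arm.

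The cost is protocol wording, some coordination within the team, and the log entry for each score. No extra patient, visit, questionnaire or staff member is asked for. Team size is not visible in the supplied text; the fallback means that no ASES contact is lost if tasks cannot be separated.

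### The surgeon is told the arm before surgery yet decides at arthroscopy, with the arm known, whether tenodesis is indicated; the sequence needs reconciling and the analysis of patients without tenodesis needs stating

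*Combined protocol and SAP*

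**What the plan says.** **When the arm is disclosed.** Section V.b.iii: "Prior to the start of the surgery, the surgeon will be notified by a member of the research team" whether the patient is in the control or the anatomic fixation group. Section IV.a confirms that the surgeon is not blinded.

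**When the indication is decided.** Section V.d.i says the initial indication is at the surgeon's discretion, and "after that decision is made, then the Control vs. intervention is determined based on our randomization scheme". Section V.d.iii, describing the diagnostic scope, says: "If there is any instability or tendinopathy, then the surgeon will decide if biceps tenotomy and tenodesis is indicated". Surgical step 2 repeats that at this point "the long head of the biceps is inspected for any instability or tendinopathy, which would be an indication to perform tenotomy". Step 2a is where the arms first diverge: "If Control group: Bicep tenotomy will occur now".

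**Whether every randomized patient has tenodesis.** Section V.c is unconditional for both groups: "The control group patient will undergo biceps tenotomy and tenodesis based on surgeon feel on appropriate tensioning of the tendon", and "Patients that are randomized to the intervention group will undergo biceps tenodesis in a standardized, step-by-step protocol as outlined below". Section V.e.i is conditional: "If indicated, patients will undergo biceps tenodesis, as described above". Inclusion (V.a.i) requires adult age, arthroscopic shoulder surgery and a listed site. Section IV.b describes the population as having pathology of the long head of the biceps tendon.

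**Who holds the list.** Section V.b.ii has each surgeon receive a stratified block list from Biostatistics, used in order of surgical start time. Section V.b.iii has a research team member announce the arm.

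**Analysis.** Section VIII names a t-test on ASES change and mixed models. It defines no analysis population and gives no rule for a randomized patient who does not have tenodesis.

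**The concern.** The decision that makes a patient informative about tensioning technique is taken, or at least confirmed, by someone who already knows the arm. If patients without tenodesis were then left out, a judgement made with the arm known would help determine who enters the primary t-test, and the groups compared would no longer be the groups randomized.

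If those patients stay in their assigned arm, exclusion bias does not arise. The effect is diluted instead. If non-indication differs between arms, the contrast also carries the effect of having no tenodesis. If the arm is revealed only after a recorded indication, neither problem arises from this source.

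A related point is foreknowledge. If V.b.ii means that a surgeon can read the list, upcoming assignments in the block can be foreseen when cases are ordered or when consent is taken on the day of surgery. This matters much less for consent in clinic, because list positions are used by surgical start time.

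**Working it through.** **1. The sequence, under both readings of V.d.i.**

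- If the initial indication is a pre-operative one, allocation can follow it and still be announced before surgery. V.d.i and V.b.iii then agree, but V.d.iii, step 2 and V.e.i leave a discretionary confirmation after disclosure.
- If it is the decision at the scope, V.d.i puts allocation after that decision and V.b.iii announces it before. The two then conflict.

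Either way V.b.iii, V.d.i and V.d.iii need to be reconciled.

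**2. The plan's own figure.** Inputs from IV.c: difference 48 − 40 = 8, SD 18, two-sided alpha 0.05, power 80%, equal-variance t-test. The noncentral t gives n = 80.44, so 81 per arm, as stated. Power is 80.3% at 81 per arm and 79.8% at 80, so there is almost no slack.

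**3. Selection, extreme case.** The documents give no rate of patients found not to be indicated, so the inputs here are assumptions. A share k of one arm is dropped and none of the other; the mean ASES change of such patients is g points below the rest; there is no true effect.

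- Bias = k × g.
- The arm that keeps them is a mixture with variance 18² + k(1 − k)g². For k = 20%, g = 20 this is 324 + 0.16 × 400 = 388.
- Numbers compared: 77, 73 or 65 against 81.

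The error rates come from simulation, so the mixture variance is carried through:

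| Share dropped in one arm | Bias, g = 10 | Type I error, g = 10 | Bias, g = 20 | Type I error, g = 20 |
|---|---|---|---|---|
| 5% | 0.5 | about 5% | 1.0 | about 6% |
| 10% | 1.0 | about 6% | 2.0 | about 10% |
| 20% | 2.0 | about 10% | 4.0 | about 24% |

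Hand check of the last cell: SE = √(324/65 + 388/81) = 3.13 and 4/3.13 = 1.28. The normal approximation gives about 25%, in line with the simulation. Holding the SD at 18 in both arms would give 26.3%, which is too high because it ignores the mixing.

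**4. Equal non-indication in both arms.** A share r has no tenodesis and, if kept, has the control mean change with SD 18. Then effect = 8(1 − r), with n = 81 per arm. If dropped, the effect stays 8 and n = 81(1 − r).

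| r | Effect if kept | Power if kept | n per arm if dropped | Power if dropped |
|---|---|---|---|---|
| 5% | 7.6 | 76.1% | 77 | 78.2% |
| 10% | 7.2 | 71.6% | 73 | 76.0% |
| 15% | 6.8 | 66.6% | 69 | 73.6% |
| 20% | 6.4 | 61.4% | 65 | 71.0% |

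**5. Consent needed if only indicated patients are randomized.** 162/(1 − r): 162/0.95 = 170.5, so 171; 162/0.80 = 202.5, so 203.

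**The case against.** The strongest reply is that the indication is mostly settled before allocation. V.d.i says so for the initial indication, and IV.b targets patients with biceps pathology, so the look at arthroscopy may only confirm. This stands as a reason to expect few such patients. It does not remove a decision made with the arm known, and neither section says what happens when the finding is not confirmed.

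Second, no passage provides for dropping anyone. IV.a randomizes patients into two groups and VIII compares those groups, so analysis as randomized is the natural reading. This also stands: silence is not a plan to exclude. It does leave the choice open until the data are in hand.

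Third, the incentive is weak. Both arms receive tenodesis, and VI.a states only 1–2 extra minutes under anesthesia for the intervention group. The selection figures are an extreme case, because only the difference in exclusion between arms produces the bias. That is accepted.

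Fourth, V.b.ii may mean only that each surgeon has a separate list, and announcement by a team member suggests the surgeon does not read it. The list point is therefore conditional.

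A reader might infer more: that the protocol plainly reverses its own order, that the arthroscopic decision is the final one, that surgeons will choose patients by arm, or that they see the list. The text supports none of these. V.d.i can be read consistently with V.b.iii, no passage calls the arthroscopic decision final, and nothing shows that selection will occur.

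**Conclusion.** The concern holds in a limited form. The plan permits a tenodesis decision made with the arm known, its sections on sequence are not reconciled, and Section VIII does not settle how a randomized patient without tenodesis is analysed. The occurrence, direction and size of any bias are unknown.

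On assumed values, one-sided exclusion of 5–20% with a 10- or 20-point gap gives a bias of 0.5 to 4 points and a type I error between about 5% and 24%. Equal non-indication of 5–20%, kept as assigned, lowers power from 80.3% to 76–61%. These ranges show what is possible and are not forecasts. The sample size of 81 per arm is correct on its own inputs.

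This should be fixed, since a small change in sequence closes the route to selection. The missing analysis population alone would be a matter of missing detail. Confidence is medium, because V.d.i and V.b.ii each bear two readings.

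**What to change.** 1. **V.b.ii.** State that Biostatistics, or a team member who neither takes consent nor sets case order, holds the list, and that the surgeons do not see it.
2. **V.b.iii and V.d.i.** State one sequence: the surgeon's decision on indication is recorded at diagnostic arthroscopy; the next concealed assignment is revealed after that and before step 2a; a patient without an indication uses no assignment.
3. **VIII.** State that every patient whose assignment was revealed is analysed in the assigned arm, whether or not tenodesis was performed.

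**Equally acceptable if reveal during surgery is impractical.** Record the pre-operative indication before the reveal and analyse everyone as assigned. This needs only wording and removes exclusion bias, at the price of some dilution (the kept column in step 4 of the working).

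**Cost.** Wording in V.b, V.d.i and VIII, and concealed envelopes or an electronic assignment for at least 162 patients. With reveal during surgery, theatre must be ready for either arm, someone already present must reveal the assignment, and more than 162 patients must be consented (171 to 203 on the assumed 5–20%). The list holder must be separate from those who take consent on the day of surgery. The clinical decision on indication stays with the surgeon.
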